## **L. Sample Size Considerations**

In order to evaluate the efficacy of BESB in this cardiac surgical population compared to those who did not receive blocks, we have defined 'efficacious' as denoting an at least 15% difference in the total opioid consumption at 96hours based on the historical rescue opiate data in the matched cohort. Assuming an alpha of 5%, 80% power, and the mean opiate requirements found in our pilot study, we estimate that a total sample size of 38 patients undergoing sternotomy with BESBs and 76 matched controls are needed to demonstrate efficacy of the new treatment (BESB).

**Table 1** (below) demonstrates that, using a 1:2 ratio of BESB:standard ERAS patients, 38 BESB and 76 standard ERAS patients are required to detect a 0.18 mean difference (15% relative reduction associated with BESB) in square-root Total (96-hr) OME between groups with 80% power using a two-sided 0.05-level test. Because the coefficient of variation for 48-hour OME is somewhat smaller, this sample size will provide 87% power to detect a 15% relative reduction (0.16 mean difference) in square-root 48-hr OME between groups using a two-sided 0.05-level test.

Because the larger SD of the two groups from background data (see **Table 2**) was used in these calculations, and because the groups will be matched on several patient characteristics which will minimize variation, these assumptions are conservative and power to detect the effect sizes shown in Table 1 may be even higher than shown.

**Table 1. Required Sample Size to Detect BESB vs. ERAS Group (1:2 Ratio) Reductions in 48- and 96-hour OME (square-root transformed) assuming two-sided  $\alpha=0.05$ , 80%/85% Power, 48-hour mean sqrt OME 1.05 and 96-hour mean sqrt OME 1.23 in ERAS Group.**

Outcome (sq. root)	SD	%Reduction	Group Difference	Power	BESB N	ERAS N
48 hr OME	0.26	15%	0.16	80%	32	64
48 hr OME	0.26	15%	0.16	85%	36	72
48 hr OME	0.26	20%	0.21	80%	19	38
48 hr OME	0.26	20%	0.21	85%	21	42
96 hr OME	0.32	15%	0.18	80%	38	76
96 hr OME	0.32	15%	0.18	85%	43	86
96 hr OME	0.32	20%	0.25	80%	20	40
96 hr OME	0.32	20%	0.25	85%	23	46

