#### Specific Aims:

1. Evaluate the utility of BESB in cardiac surgical patients by assessing the pain scores, opioid consumption, and complications related to BESB.
2. Compare intra- and postoperative opioid use in patients receiving BESB vs. matched historical controls who did not receive BESB in the ERAS program.
3. Compare clinical outcomes between the 2 groups: duration of mechanical ventilation, time to mobilization, pain scores (median pain score per period), intensive care unit length of stay (LOS), incidence of postoperative nausea and vomiting, postoperative complications, hospital LOS, readmissions, mortality, recovery to baseline activity and sleep post discharge, total and rescue opioid pain medication requirements.
4. Evaluate quality of sleep and activity with (Fitbit™) smart watch device of patients receiving BESB during the postoperative period.

**Hypothesis:** The investigators hypothesize that BESB is efficacious with respect to pain control and will lead to a 15% or greater reduction of consumed opiate equivalents at 12, 24 and 48 hours, and the 24-hour period preceding both 72 and

96 hours postoperatively compared to matched historical controls who received standard of care pain management (systemic opioid therapy).

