Indeed, given these considerations, our group recently investigated the feasibility of performing these blocks bilaterally in a pediatric cardiac surgical population undergoing sternotomy-based procedures (IRB-P00031524). At the conclusion of this 10-patient pilot, our group found that performing these blocks was technically feasible, requiring 30 minutes or less of OR time, resulting in no known complications. Furthermore, our data suggested an approximate 25% reduction in rescue opioid requirements in the first 48 hours amongst the erector spinae group ( $p=0.048$ ).

During the short time required to complete our pilot study, several additional adult studies of improved size and quality have been published demonstrating favorable outcomes with this block for a variety of indications, including post-sternotomy care. As such, it has effectively become an accepted practice in the larger community and here at BCH as well, with surgeons, anesthesiologists, and families frequently requesting an ESB (unilateral or bilateral) as a part of the care they either provide or receive. We believe we have reached a point of clinical equipoise in relation to the existing standard of systemic opioid therapy and seek to evaluate the relative efficacy of this technique in a pediatric cardiac surgical population at BCH.

In order to best evaluate the efficacy of this block in the pediatric cardiac population, a blinded, randomized and controlled trial would be ideal. However, given that randomization could be challenging and the fact that blinding would not be feasible, we believe an observational prospective cohort study is most appropriate at this time.

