As such, we propose to evaluate the comparative efficacy of BESB versus matched historical controls who received standard of care pain management (systemic opioid therapy) for patients undergoing cardiac surgery via sternotomy by means of a single arm, open label, interventional study that will compare as the primary outcome rescue analgesic requirements, rendered as opiate equivalents, at 12, 24 and 48 hours, and the 24 hour period preceding both 72 and 96 hours postoperatively. 'Efficacy' will be considered as a threshold of clinical significance being defined as a 15% difference). In addition to the primary endpoint, we plan to evaluate the duration of intubation, length of ICU stay, median pain scores, incidence of PONV (postoperative nausea and vomiting; 0-6h, 6-12h and overall), time to mobilization and adverse events between these groups. Postoperative data collected from standard clinical follow-up tools, such as return to baseline sleep and activity status as well as pain medication requirements at home, will also be compared. In addition, we plan to evaluate the quality of sleep and activity with a smart watch (Fitbit™) during the perioperative period in the BESB group only.

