## **E. Definition of Primary and Secondary Outcomes/Endpoints**

### **Primary:**

- Analgesic requirements, rendered as opiate equivalents, at 12, 24 and 48 hours, and the 24 hours preceding both 72 and 96 hours postoperatively.

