## **K. Data Analysis Plan**

At the time of data analysis, de-identified datasets will be downloaded from the secure database and merged into secure statistical analysis tool for purposes of analysis. Missing data will be accounted for when the data is coded into respective variables.

Descriptive statistics will be generated in order to summarize demographic characteristics of patients enrolled. Data will be tested for normality using the Shapiro-Wilk test. Data will be presented as total n (%), means and standard deviations (SD) if the distribution appears normal, or medians and range when not.

Assuming normality, t-tests will be conducted to investigate the differences between the two exposure groups (to compare total opioid equivalents, time required to place the block, time to extubation, and time to discharge, etc.). If data does not appear to be normal, Wilcoxon Rank Sum/Mann-Whitney tests will be used for group comparisons. Repeated measure analysis will be used to compare pain scores over time between groups and when compared to baseline values. Adverse events and complications (if any) associated with the blocks will be recorded and categorized. Fisher's exact test will be used to compare the proportion of patients who reported adverse events between the two groups.  $P<0.05$  will be considered statistically significant.

Should a clinically significant effect be demonstrated, healthcare costs related to the surgical encounter for both groups will be approximated and compared in order to better assess the added value of the intervention in a more global fashion.

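### Section L defines efficacy as a 15% difference in 96-h opioid consumption, but 38/76 gives 80% power only for 15% on the square-root scale, which is about a 26-28% cut in consumption under the planning SD

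*Combined protocol and SAP*

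**What the plan says.** Section L sets the efficacy criterion as "at least 15% difference in the total opioid consumption at 96hours" and states that "38 patients undergoing sternotomy with BESBs and 76 matched controls are needed to demonstrate efficacy of the new treatment". The next paragraph and Table 1 obtain 38/76 as the number needed "to detect a 0.18 mean difference (15% relative reduction associated with BESB) in square-root Total (96-hr) OME": 15% of a square-root mean of 1.23, with SD 0.32, two-sided 0.05 and 1:2 allocation. The same section claims 87% power for 15% on square-root 48-hour OME.

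Elsewhere the 15% is attached to opioid amounts with no transformation named. The hypothesis in Section A is a "15% or greater reduction of consumed opiate equivalents at 12, 24 and 48 hours" and in later windows. Section B gives a "threshold of clinical significance being defined as a 15% difference" for rescue requirements expressed as opiate equivalents.

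Section K applies t-tests if the data look normal, "to compare total opioid equivalents, time required to place the block, time to extubation, and time to discharge" among other outcomes, and Wilcoxon rank-sum tests otherwise. It does not mention the square root.

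**The concern.** A percentage change in a mean square root is not the same percentage change in the mean. The efficacy sentence and the sample-size sentence use one 15% for two effects of different size, and the larger effect is the one that was powered.

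A reader who takes the efficacy sentence together with the sample size would credit the study with 80% power for a 15% cut in consumption. A non-significant result could then be taken as good evidence against a cut of that size. Section N says the results may lead to a randomized trial, so the misreading could carry over into its sizing.

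**Working it through.** **Inputs.** Section L and Table 1: square-root 96-h difference 0.18, SD 0.32, 38/76, two-sided 0.05. Table 2, 96 h, mean (SD): square-root OME 1.231 (0.211) ERAS and 1.120 (0.320) BESB; OME 1.557 (0.540) ERAS and 1.346 (0.724) BESB. Enrolment target 45/90. Power is from the noncentral t, pooled for equal SDs and with Welch degrees of freedom for unequal SDs.

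**1. The plan's own figure.** 0.15 × 1.23 = 0.1845, entered as 0.18. SE = 0.32 × √(1/38 + 1/76) = 0.0636; 0.18/0.0636 = 2.83; power 80.1%. At 48 h, 0.16 with SD 0.26 gives 86.7%, against the stated 87%. Both reproduce.

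**2. What 15% on the square-root mean is in consumption.** Mean OME = (square-root mean)² + (square-root SD)². Check: 1.231² + 0.211² = 1.560, against 1.557 in Table 2. The reduced square-root mean is 0.85 × 1.231 = 1.046.
- Uniform proportional effect: 1 − 0.85² = 27.75%.
- SD 0.32 in both groups: 1.618 to 1.197, a cut of 26.0%.
- Pilot SDs (ERAS 0.211, BESB 0.320): 1.560 to 1.197, a cut of 23.2%.

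**3. Power for a true 15% cut in 96-h consumption.** The square-root difference is:
- Proportional effect: 1.231 × (1 − √0.85) = 0.096.
- SD 0.32 in both groups: 1.231 − √(0.85 × 1.618 − 0.32²) = 0.103.
- Pilot SDs: 1.231 − √(0.85 × 1.560 − 0.32²) = 0.125.

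On untransformed OME the difference is 0.15 × 1.557 = 0.234. A single SD below applies to both groups; pairs are BESB/ERAS.

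| Assumption | Difference | SD | 38/76 | 45/90 |
|---|---|---|---|---|
| Planning SD, proportional effect | 0.096 | 0.32 | 32% | 37% |
| Planning SD in both groups | 0.103 | 0.32 | 36% | 42% |
| OME, larger SD | 0.234 | 0.724 | 36% | 42% |
| Pilot SDs for the conversion, planning SD for the test | 0.125 | 0.32 | 50% | 56% |
| Pilot SDs throughout | 0.125 | 0.320/0.211 | 57% | 65% |
| OME, pilot SDs | 0.234 | 0.724/0.540 | 41% | 47% |
| ERAS SD, proportional effect | 0.096 | 0.211 | 62% | 70% |
| OME, ERAS SD | 0.234 | 0.540 | 58% | 65% |
| ERAS SD, BESB SD shrunk proportionally | 0.096 | 0.195/0.211 | 67% | 74% |
| OME, ERAS SD, BESB SD shrunk proportionally | 0.234 | 0.459/0.540 | 66% | 74% |

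The 45/90 column assumes no withdrawals. The 26-28% equivalents belong with the 32-36% rows. The 23% equivalent belongs with the 50% and 57% rows.

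**4. Wilcoxon branch.** In 10,000 simulations with normal square-root OME truncated at 0 and a 15% proportional cut, power at 38/76 and 45/90 was 31%/35% (SD 0.32), 60%/67% (SD 0.211) and 63%/70% (SDs 0.195/0.211).

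**5. SD needed for 80%.** With equal SDs, the square-root SD would have to be 0.171 at 38/76 or 0.186 at 45/90. With the BESB SD shrunk, the ERAS SD would have to be 0.180 or 0.196. The plan used 0.32; the smaller pilot SD is 0.211.

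**6. The gap in Table 2, and 48 h.** From ERAS to BESB at 48 h, mean OME falls by 1 − 0.854/1.134 = 24.7% and mean square-root OME by 1 − 0.890/1.050 = 15.2%. At 96 h the falls are 1 − 1.346/1.557 = 13.6% and 1 − 1.120/1.231 = 9.0%. The scale point applies to the 48-h sizing too: power for a 15% consumption cut at 38/76 is 35% (0.082, SD 0.26) or 36% (0.170, SD 0.528).

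**The case against.** **The scale is disclosed.** The sample-size paragraph and Table 1 both say square root, so nothing is concealed and Table 1 contains no arithmetic error. This stands. It does not change the efficacy definition in the preceding paragraph, which is on consumption and is the one that 38/76 is said to serve.

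**The planning SD is deliberately conservative.** Section L says so, and the larger SD comes from only 10 BESB patients. A reader might infer that power for a 15% cut simply is about a third. The documents do not support that: 32-36% is the low end, and Table 2 SDs take it to about 67%. Section L's conservatism claim concerns the effect sizes in Table 1, which are square-root effects. One combination does pass 80%: a difference of 0.125 tested with SD 0.211 in both groups gives 84%. It contradicts itself, because 0.125 arises only if the BESB SD is 0.320.

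**Matching will reduce variation.** It may, and at 45/90 the SD would need to fall only from 0.211 to about 0.196 in the most favourable case. But the documents give no correlation, and the tests named in Section K are unpaired.

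**The hypothesis is 15% or greater.** True: larger effects are better powered, and the 48-h pilot difference matches the effect sized for. The 96-h pilot difference was smaller.

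**The pilot's rescue-opioid result.** A reader might treat "our data suggested an approximate 25% reduction in rescue opioid requirements in the first 48 hours" as the same result as the 24.7% in Table 2. No section says they are the same measure. The text concerns rescue opioids with p = 0.048, whereas pooled t-tests on Table 2 at 48 h give p = 0.11 (OME) and 0.059 (square root). The point does not rely on that link.

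**Cumulative 96-h OME is not a listed primary outcome.** Section E lists "Analgesic requirements, rendered as opiate equivalents, at 12, 24 and 48 hours, and the 24 hours preceding both 72 and 96 hours postoperatively". So the point concerns Section L's efficacy criterion and, by the same argument, the 48-h sizing. It says nothing about power in the other windows.

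**Conclusion.** The statement in Section L is wrong as written: 38/76 does not give 80% power for the efficacy criterion that the section defines. It gives 80% for an effect of about 26-28% in mean consumption under the planning SD, or about 23% under the unequal pilot SDs.

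For a true 15% cut in 96-h consumption, t-test power at 38/76 is about 32-36% under the planning SD and about 32-67% across the Table 2 SDs; at 45/90 it is about 37-74%. No consistent set of SDs tried reaches 80%, though none is offered as an upper limit. The figures rest on Table 2 means and SDs from 20 and 10 patients, unpaired tests, no withdrawals at 45/90, and no allowance for matching.

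Section K's silence on scale matters only if the t-test is used, because a rank test gives the same result on either scale. It does not follow that the sample size must rise.

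**What to change.** - **Section L:** state that the 80% applies to a 15% reduction in mean square-root 96-h OME, about a 26-28% cut in consumption under the planning SD. Add that power for a 15% cut in consumption is about 32-36% under the planning SD and about 32-67% at 38/76 across the Table 2 SDs, with no allowance for matching.
- **Sections A, B and L:** put the 15% threshold on one named scale.
- **Section K:** name for the opioid t-test the scale used in the power calculation (the Wilcoxon test needs no change), and report the percentage reduction in OME with a 95% CI.

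This is wording only: no extra patients and no added data. The cost is a less favourable stated power for a 15% reduction in consumption.

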**Table 2. Background Data**

Group	N	Obs	Variable	N	Mean	Std Dev	Median
ERAS	20	sqD0N0D1N1	20	1.050	0.181	1.049	
		sqtotolome	20	1.231	0.211	1.227	
		D0N0D1N1_OME	20	1.134	0.390	1.100	
		Total_OME	20	1.557	0.540	1.505	
BESB	10	sqD0N0D1N1	10	0.890	0.261	0.898	
		sqtotolome	10	1.120	0.320	1.157	
		D0N0D1N1_OME	10	0.854	0.528	0.810	
		Total_OME	10	1.346	0.724	1.340	

Given the possibility of patient withdrawal due to procedural changes, intraoperative exclusionary events, etc., we plan to enroll 45 patients for the BESB intervention group and 90 matched historical controls from the cardiac ERAS database (IRB P00029161).

## **N. Potential Benefits**

It is possible that, as a result of receiving these blocks, a patient might a) be exposed to less narcotic and benzodiazepine than might otherwise be the case, b) be extubated sooner and as such be at less risk for ventilator-associated pneumonia, and/or c) mobilize earlier and therefore avoid numerous possible postoperative complications. These are just putative benefits known to be associated with regional anesthetics and thus may occur in study participants.

Results from our pilot study suggested an approximate 25% reduction in opioid requirements in the first 48 hours following surgery, but the study was too small to draw any significant conclusions. Currently no data exists to recommend these blocks over conventional management in congenital cardiac surgery via a median sternotomy. The results of this study may allow the investigators to develop an appropriately powered, randomized controlled trial to evaluate the utility of this intervention which might be used to inform such management decisions for future patients.

## **O. Privacy Provisions**

Information will only be made available to individuals who are part of the research team. Medical information collected for this study will only become part of the child's medical record if the information is determined to be pertinent to the care the child is receiving at Boston Children's Hospital. Disclosure of personal information may occur only when required by law.

## **P. Confidentiality Provisions**

All identifying information such as dates of birth, names, and medical record numbers will be removed from the study database. All patients will be assigned an ID number that will not be linked to any patient identifying information. All data will be electronically secured in a password protected private folder. Only research investigators and personnel affiliated with the study will have access to patient information.

Every effort will be made by research staff to keep patient information confidential. To ensure patient confidentiality, all research data will be secured in locked filing

cabinets in a locked office. Any publications that result from this study will not be linked with personal identifiable information that would disclose the identity of study subjects.

